5.2 Volume and ICRU Reference Point Definitions

5.2.1 The Gross Tumor Volume (GTV) is defined as all gross disease determined from CT, clinical information and endoscopic findings. T1a tumors are small by definition. There are tumors for which a GTV will not be readily available on the CT scan due to small size of the tumor or gross tumor extirpation by a biopsy procedure. For patients where a clear GTV is not evident, no GTV volume will be defined

5.2.2 The Clinical Target Volume is defined as the area thought to contain gross disease and areas potentially at risk for microscopic disease. Regardless of whether a GTV is evident on imaging, the CTV will be very similar for every patient

5.2.2.1 Superior border: Superior extent of the arytenoid cartilage

5.2.2.2 Inferior border: Inferior extent of the true vocal fold

5.2.2.3 Lateral border: Outer aspect of the ipsilateral thyroid cartilage

5.2.2.4 Medial border: Air within the larynx at the midline of the body

5.2.2.5 Anterior: Volume will completely treat the anterior commissure and up to the anterior 1/3 of the contralateral vocal fold, in order to minimize the risk of marginal miss

5.2.2.6 Posterior border: Posterior aspect of the arytenoid cartilage. Inferiorly, the arytenoid cartilage will not be visible on slices that extend to the inferior extent of the true vocal fold. The posterior border in this region should include the ipsilateral portion of the cricoid cartilage immediately inferior to the arytenoid and the adjacent ipsilateral cricoarytenoid musculature

5.2.3 The Planning Target Volume (PTV) will provide a margin around the CTV to compensate for the variabilities of treatment setup and internal organ motion. An asymmetric PTV will be employed due to concerns of deglutition preferentially displacing the larynx in the superior/inferior and anterior/posterior orientations. Mid-neck anatomy does not allow for a 10 mm anterior/posterior margin. Thus 5 mm was chosen

5.2.3.1 Superior/inferior PTV expansion: 10 mm

5.2.3.2 Anterior/Posterior 5 mm

5.2.3.3 Medial/Lateral: 3 mm

5.2.4 After completion of contouring as detailed in 5.2.2 and 5.2.3 the superior/inferior extent of the PTV will be measured. If it measures less than 4.0 cm, it will be extended to such a length (the typical treated length for standard therapy) by copying and extending the most superior and most inferior contour superiorly and inferiorly (respectfully) until a 4 cm field is achieved.

5.3 Targets and Critical Normal Tissue Definitions

5.3.1 Targets

5.3.1.1 There will be a single target for this protocol – a single PTV. There will be no elective nodal irradiation

5.3.2 Dose

5.3.2.1 Tis and T1a: 63 Gy in 28 fractions T2a: 65.25 Gy in 29 fractions

5.3.3 Critical Normal Tissue Structures

5.3.4. GSL

5.3.4.1 A secondary volume of GSL – PTV will be created. This will be defined as the glottic and supraglottic larynx, including the tip of the epiglottis, the aryepiglottic folds, arytenoids, false cords, and true cords, bounded by the thyroid cartilage laterally, anteriorly the anterior edge of the pre-epiglottic fat, and posteriorly bounded by the anterior edge of the pharyngeal wall or the posterior edge of the arytenoid and/or cricoid cartilage.

5.3.5 Contralateral arytenoid

5.3.5.1 The arytenoids are small, 3-sided pyramidal structures that sit superior to the cricoid cartilage in the posterior larynx. They are small (mean volume estimated at 0.312 cc). An attached supplement demonstrates 2 contouring examples. No attempt will be made to differentiate the arytenoid and corniculate cartilage

5.3.6 Ipsilateral carotid artery

5.3.6.1 Both carotid arteries will be contoured on all slices that include a PTV plus 1-2 slices above and below.

5.3.7 Contralateral carotid artery

5.3.8 Spinal Cord

5.3.8.1 The cord will be contoured on all slices that include a PTV plus 1-2 slices above and below

5.3.9 Inferior pharyngeal constrictor

5.3.9.1 Defined as the pharyngeal musculature beginning at the level of the inferior hyoid superiorly and extending to the esophageal verge inferiorly.

5.3.10 Esophageal verge

5.3.10.1 Extending superiorly from the inferior pharyngeal constrictor extending inferiorly to the most inferior level with a PTV contour

5.4 Planning

5.4.1 The treatment for each patient will be inverse planned. Either step-and-shoot intensity modulated radiation therapy (IMRT) or volumetric arc therapy (VMAT) will be employed. If step-and-shoot IMRT is employed, beams that enter through the contralateral arytenoid should be avoided to help with dosimetric goals.

5.4.2 Dose specification

5.4.2.1 95% of the PTV will receive the prescription dose

5.4.2.2 $\geq 99.5\%$ of the PTV will receive 95% of the prescription dose

5.4.2.3 $< 1\%$ of the PTV will receive $> 110\%$ of the prescription

5.4.2.4 Prescription will be 63 Gy in 28 fractions (T1a and dTis) or 65.25 Gy in 29 fractions

5.4.3 Critical Normal Tissue Structures Guidelines

Spinal cord: < 25 Gy; deviation acceptable < 30 Gy

5.4.3.1 Contralateral Arytenoid: Mean Dose ≤ 21 Gy

5.4.3.2 Ipsilateral carotid artery: < 45 Gy

5.4.3.3 Contralateral carotid artery < 10 Gy

5.4.3.4 Spinal cord: 0.1 cc < 20 Gy

5.4.3.5 Inferior pharyngeal constrictor: Mean Dose < 31.5 Gy

5.4.3.6 Esophageal Verge: < 20 Gy

5.4.4 Doses are prescribed as above. IMRT prescribing requires prioritization. Prioritization for this investigation is as below:

5.4.4.1 PTV 63

5.4.4.2 Contralateral arytenoids

5.4.4.3 Inferior pharyngeal constrictor

5.4.4.4 Esophageal verge

5.4.4.5 Spinal cord

5.4.4.6 Contralateral carotid artery

5.4.4.7 Ipsilateral carotid artery

5.5 External beam equipment and beam delivery methods

5.5.1 4 or 6 MV beams are required

5.6 Daily Treatment Localization/IGRT

5.6.1 Daily image guidance (IGRT) is required. This may be achieved with the following technique:

5.6.1.1 Linear accelerator mouth kV and MV conebeam CT images

5.6.1.2 CT on rails images

5.6.2 Treatment day procedure to register the imaging dataset are as follows:

5.6.2.1 Region of interest (ROI) for fusion is the larynx

5.6.2.2 Both manual and automatic types of registration can be used.

5.6.2.3 The result of the fusion must be visually checked for the alignment of the cartilages of the larynx (thyroid and cricoid cartilage) and the adjacent bony anatomy (cervical spine).

5.6.2.4 In the instance of a disagreement between cartilage and spine alignment, cartilage alignment will be prioritized

5.6.2.5 Following the registration, the translational corrections will be applied to the treatment couch. If one or more corrections are larger than 5 mm, imaging must be repeated.

5.6.2.6 Special consideration of first fraction of radiation: If one or more corrections are larger than 10 mm, it will be assumed that the patient was swallowing during acquisition and the image will be repeated. If the repeat image similarly requires a larger than 10 mm, the start of radiation will be cancelled for that day. The same treatment localization will then be performed on the next clinic day. Should a shift larger than 10 mm be required again, it will be assumed that the patient was swallowing during the CT simulation acquisition, introducing a systematic error. In this situation, a new CT simulation and a new treatment plan will be required.

5.7 Concomitant Medications, Supportive Care, Excluded Therapies and Restrictions

Patients should receive full supportive care therapies concomitantly during the study when appropriate. Any disease progression requiring other forms of specific anti-tumor therapy will be cause for early discontinuation of study treatment.

Use of concurrent investigational agents is not permitted.

5.8 Duration of Therapy

In the absence of treatment delays due to adverse events, patients will receive 6 weeks of treatment unless one of the following criteria applies:

- Disease progression
- Intercurrent illness that prevents further administration of treatment
- Unacceptable adverse events
- Patient becomes pregnant
- Patient decides to withdraw from the study or
- General or specific changes in the patient's condition that render the patient unacceptable for further treatment in the judgment of the investigator.

5.9 Duration of Follow up

Patients will be followed for 24 months after completion of radiation. Patients removed from study for unacceptable adverse events that are related to the study treatment will be followed until resolution or stabilization of the adverse event.

5.10 Criteria for Discontinuation

Patients will be removed from study when any of the criteria listed in Section 5.8 applies. The reason for study removal and the date the patient was removed must be documented in the medical record and case report form.

6.0 Risks to Participants

Limited field radiation may not be as successful as whole larynx RT and there may be an increased risk of treatment failure

It is unknown if unilateral radiation introduces asymmetric function in the larynx. However, single vocal cord targeted therapy (surgery) causes no noticeable asymmetric symptoms³ (reduced comfort and exacerbated throat clearing), so the risk is anticipated to be small

7.0 Potential Benefits to Participants

Patients will have more dedicated follow-up with laryngology – this potentially will lead to better post-treatment function.

Patients will receive therapy to a smaller volume, and potentially have improved functional outcomes as a consequence.

8.0 Cost to Participants

There are no unanticipated costs to participants in this trial. IMRT is a covered service by insurance/Medicare in the treatment of larynx cancer. Stroboscopy is a covered service for the follow-up of patients with larynx cancer.

9.0 Study Calendar

	Screening	Pre-TX	WK 1 RT	WK 2 RT	WK 3 RT	WK 4 RT	WK 5 RT	WK 6 RT	TREATMENT COMPLETE	1 Month	3 Month	6 Month	9 Month	12 Month	16 Month	20 Month	24 Month
Medical History ^c	X																
Physical Exam ^c	X																
Vital Signs ^{b,c}	X									X	X	X	X	X	X	X	X
Performance Status ^c	X									X	X	X	X	X	X	X	X
Pregnancy Test ^a		X ^a															
CT Neck ^c		X															
CT Simulation		X															
Informed Consent ^c	X																
Video Stroboscopy and Functional Assessment ^d		X								X							X
Patient Questionnaire – EAT-10		X								X	X	X		X			X
Adverse Event Evaluation										X	X	X	X	X	X	X	X
IMRT			X	X	X	X	X	X									
A) A Serum pregnancy test must be performed on WOCBP within 14 days prior to exposure to radiation. The first study-related exposure is at the time of the CT scan of the neck. B) Vital signs include temperature, blood pressure, pulse, respiration rate C) All screening procedures must be obtained within 30 days of registration. D) During the assessment the following forms will be completed: -Voice Handicap Index (VHI) -Grade, roughness, breathiness, asthenia, and strain (GRBAS) scale -Penetration aspiration scale (PAS)																	

10.0 Adverse Events

10.1 Definitions

10.1.1 Adverse Events (AE) is any unfavorable and unintended sign (including an abnormal laboratory finding), symptom or disease temporally associated with the use of a medicinal (investigational) product, treatment or procedure regardless of whether it is considered related to the medical treatment or procedure (*NCI CTEP Guidelines March 28, 2011*)

10.1.2 Serious Adverse Event (SAE) is an AE that is fatal or life threatening, requires inpatient hospitalization or prolongation of existing hospitalization (for > 24 hours), persistent or significant incapacity or substantial disruption of the ability to conduct normal life functions, or is a congenital anomaly/ birth defect, or results in any important medical event that may not result in death, be life threatening, or require hospitalization may be considered an SAE when, based upon appropriate medical judgment, may jeopardize the subject and may require medical or surgical intervention to prevent any of the above outcomes. A “life-threatening” adverse event places the patient at immediate risk of death in the judgment of the investigator or sponsor.

10.1.3 Severity Rating

The investigator will evaluate the severity of each adverse event. NCI Common Terminology Criteria for Adverse Events (CTCAE v.4.0) or study specific toxicity tables provided in the protocol define severity. If not included in CTCAE v.4.0, severity is expressed in numerical grade using the following definitions:

1. Grade 1: Mild-asymptomatic or mild symptoms; clinical or diagnostic observations only; intervention not indicated.
2. Grade 2: Moderate-minimal, local or noninvasive intervention indicated; limiting age appropriate instrumental ADL.
3. Grade 3: Severe-severe or medically significant but not immediately life-threatening; hospitalization or prolongation of hospitalization indicated; disabling; limiting self care ADL.
4. Grade 4: Life-threatening consequences; urgent intervention indicated.
5. Grade 5: Death related to AE

10.1.4 Attribution/Relationship to study drug

1. Definite – clearly related
2. Probable – likely related
3. Possible – may be related
4. Unlikely – doubtfully related
5. Unrelated – clearly not related

10.1.5 Expectedness

An Expected Adverse Event is one where the specificity or severity is consistent with the current information available from the resources.

An Unexpected Adverse Event is one where the nature, severity, or frequency of the event is related to participation in the research is not consistent with either:

1. The known or foreseeable risk of adverse events associated with the procedures involved in the research that are described in (a) the protocol-related documents, such as the IRB-approved research protocol, any applicable investigator brochure, and the current IRB-approved informed consent document, and (b) other relevant sources of information, such as product labeling and package inserts: or
2. The expected natural progression of any underlying disease, disorder, or condition of the subject (s) experiencing the adverse event and the subjects(s) predisposing risk factor profile for the adverse event.
(OHRP Guidance on reviewing unanticipated problems 2007)

10.2 Recording and Reporting Responsibilities

10.2.1 Investigative site recording responsibilities:

1. Upon identification of an AE or SAE, the site investigator will utilize the above definitions to properly classify the event. Each category listed above must be recorded for each event.
2. All AEs and SAEs will be recorded in the “AE case report forms” (CRF) and in progress reports with details about the grade and attribution of each episode, action taken with respect to the study drug, and the patient’s outcome will be recorded in the CRF. All events will be recorded on case report forms for the duration of the study until they resolve.
3. All SAEs will be recorded on the FDA MedWatch form 3500a. After submitting the initial report it may be necessary to submit follow up reports to the ISRU, Sponsor and the FDA should the event require further investigation.

10.2.2 Investigative site reporting responsibilities:

1. The investigator/ site is responsible to report all SAEs to the ISRU within 24 hours of becoming aware of the event. A written report must follow within 48 hours.

2. Each investigator is responsible to report all AEs/SAEs to their local IRB following guidelines set by that IRB. The FCCC OCR reserves the right to request an event be reported to the IRB at their discretion. Copies of events reviewed by the IRB must be emailed to [contact].
3. If the investigator or IRB feels the event warrants a revision to the informed consent that was not already initiated by the ISRU, draft revisions will be made in track changes and submitted to the ISRU for consideration. Any consent revisions must receive ISRU approval **prior** to submission to the IRB.
4. Any investigator who is in doubt of whether a particular AE needs to be reported is directed to call the FCCC ISRU for confirmation with the Principal Investigator
5. If the results of an investigator or OCR investigation show an adverse event not initially determined to be reportable is so reportable, the investigator will report the event following the above guidelines based on the date the determination is made.
6. Copies of all related correspondence and reporting documents must be submitted to the ISRU and will be maintained in a regulatory file.

The participating site should report events to:

Investigator-Sponsored Research Unit
Office of Clinical Research
Fox Chase Cancer Center
[contact]

10.2.3 OCR Reporting Responsibilities:

1. Adverse events which meet all of the following criteria must be reported to all participating institutions for IRB submission within 2 weeks of notification of the event.
 - i. Unexpected (in terms of nature, severity, or frequency) given (a) the research procedures that are described in the protocol-related documents, such as the IRB-approved research protocol and informed consent document; and (b) the characteristics of the subject population being studied;
 - ii. Possibly related to participation in the research (possibly related means there is a reasonable possibility that the incident, experience, or outcome may have been caused by the procedures involved in the research); and

- iii. Serious (refer to above definition) or otherwise one that suggests that the research places subjects or others at a greater risk of physical or psychological harm than was previously known or recognized.
2. If the adverse event requires modification of the study protocol and informed consent, these changes will be provided to all participating institutions in the form of an amendment from the OCR for each site's IRB of record along with the report of the adverse event.
3. Copies of all related correspondence and reporting documents will be maintained in a centralized regulatory file for this study at ISRU.

10.3 Pregnancy

All WOCBP should be instructed to contact the Investigator immediately if they suspect they might be pregnant (e.g., missed or late menstrual period) at any time during study participation.

In the event of a confirmed pregnancy in a patient participating in the study, the Investigator must immediately notify the Fox Chase Cancer Center Investigator-Sponsored Research Unit.

11.0 Statistical Analysis

This is a single arm phase II trial. Prior head and neck investigations of IMRT to minimize 3D conformal toxicity have anticipated (and demonstrated) a 30% decrease in symptoms when IMRT is utilized³⁸. Non-randomized analyses have suggested that the benefit of IMRT approaches a 50% decrease in symptoms³⁹. Thus, to be conservative, the null hypothesis of this analysis is that two year VHI scores will be 33% lower than baseline. This represents a decline from an average VHI global score of 44 to about 29, a decline of 15 points. Our alternative of interest is a 50% decline in VHI global score, a decline of 22 points. L. Di Nicola et al (ref) tabulated such scores and we have taken their estimate of the standard deviation at baseline of VHI global score, std = 8.5. We used this same value for the 2 year score, which is not given by Di Nicola, but is close to the 3 year score when VHI scores have further declined. This, in turn, gives the std of baseline less 2 year scores of 8.5 times 1.414. VHI average scores are estimated to be normally distributed.

We will obtain baseline and 2 year VHI scores for an initial cohort of 15 patients. We will terminate the study after the first 15 patients have been evaluated at 2 years if their average decline is less than 15. Otherwise we will recruit an additional 15 patients. If the overall average of all 30 patients is at least 19.2 we will reject the null hypothesis. The design has 50% chance of early stopping under the null and a 2.58% chance of early stopping in error. The overall type I error is 5% and the study power is 85%.

We will test the null hypothesis that at most 85% of patients will achieve local control versus the alternative that at most 95% of them will. If less than 13 of the initial cohort

of 15 experience local control, we will interrupt the study for futility. If at least 28 of 30 acquire local control we will reject the null and declare the local control rate to be 95%. The chance of early stopping for lack of local control is 40% when the true local control rate is 85%. The chance of early stopping in error is 3.6%. The overall power is 81% and overall type I error is 15.1%.

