2.0 Objectives

To define a new treatment technique for T1a larynx cancer that maintains excellent local control with less extensive radiation fields

Hypothesis: Contralateral arytenoid sparing IMRT for T1a larynx cancer maintains the excellent local control associated with whole larynx radiation and results in functional outcomes at 24 months after therapy that are suggestive of improved function when compared to historical controls

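### The VHI null of a 15-point fall from baseline is not tied to any result after whole-larynx radiation, so rejecting it does not by itself support improved function against historical controls

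*Combined protocol and SAP*

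**What the plan says.** Section 11.0 builds the voice hypothesis in three steps.

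- It cites head and neck "investigations of IMRT to minimize 3D conformal toxicity have anticipated (and demonstrated) a 30% decrease in symptoms when IMRT is utilized".
- It adds a larger figure: "Non-randomized analyses have suggested that the benefit of IMRT approaches a 50% decrease in symptoms".
- It then concludes: "Thus, to be conservative, the null hypothesis of this analysis is that two year VHI scores will be 33% lower than baseline". In points, "This represents a decline from an average VHI global score of 44 to about 29, a decline of 15 points". The alternative follows: "Our alternative of interest is a 50% decline in VHI global score, a decline of 22 points".

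The test uses baseline minus 2-year scores in a single arm. The trial stops if the first 15 patients have a mean fall below 15, and rejects the null if the mean fall over 30 patients is at least 19.2.

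The hypothesis in Section 2.0, repeated in 2.4, concerns "functional outcomes at 24 months after therapy that are suggestive of improved function when compared to historical controls". The primary endpoint under Section 2.2 asks for a 50% VHI improvement at 24 months and names no comparator.

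On the radiotherapy voice series that supplies the SD, Section 11.0 says that the 2-year value is not given, "but is close to the 3 year score when VHI scores have further declined".

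**The concern.** The cited percentages and the null are on different scales. The 30% compares IMRT with 3D conformal treatment. The 50% is described as a benefit of IMRT, which also reads as a comparison between techniques. The null and alternative are changes within the patient from before to after treatment. A fall from baseline contains whatever tumour clearance and recovery would produce under any radiation technique, plus any gain from sparing the contralateral arytenoid. Section 7.0 adds a further contributor: closer laryngology follow-up, which it says may itself improve function.

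In a single-arm trial, the null value is where a historical control can enter the test. If that value does not represent the historical result, the test cannot speak to the comparison in Sections 2.0 and 2.4. At stake is what a positive VHI result may be said to mean.

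**Working it through.** **Inputs (all Section 11.0).** Baseline mean 44; null fall 15; alternative fall 22; SD of one score 8.5; SD of change 8.5 × 1.414 = 12.02; stage 1 n = 15 with cut-off 15; total n = 30 with cut-off 19.2. The 2-year fall after whole-larynx radiation is not in the documents and is varied below as an assumption.

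**Step 1: points.** 33% of 44 is 14.5, and one third of 44 is 14.7; the plan rounds to 15. Half of 44 is 22. The final cut-off of 19.2 is 19.2/44 = 43.6% of baseline.

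**Step 2: the two scales.** Suppose whole-larynx patients fall by a fraction f from 44, and IMRT lowers the 2-year score by a further fraction r. The fall from baseline with IMRT is then 44 − 44(1 − f)(1 − r).

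| Assumed f | Whole-larynx 2-year score | Fall with IMRT, r = 30% | Fall with IMRT, r = 50% |
|---|---|---|---|
| 0 | 44 | 13.2 | 22.0 |
| 20% | 35.2 | 19.4 | 26.4 |
| 33.3% | 29.3 | 23.5 | 29.3 |

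A between-technique reduction equals a fall from baseline only when f = 0, that is, when whole-larynx patients do not improve at all. If they improved by a third, the cited benefits would mean falls of 23.5 to 29.3 points, above the 22-point alternative.

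**Step 3: the plan's own operating characteristics.** Write μ for the true mean fall. The standard errors are 12.02/√15 = 3.10 (stage 1) and 12.02/√30 = 2.19 (overall). The two means have correlation √(15/30) = 0.707. Then

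P(success) = P(mean of 15 ≥ 15 and mean of 30 ≥ 19.2) = Φ₂(a, b; 0.707), with a = (μ − 15)/3.10 and b = (μ − 19.2)/2.19.

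| Quantity | Stated | Recomputed, SD 12.02 | Recomputed, SD 14 |
|---|---|---|---|
| Early stop, μ = 15 | 50% | 50.0% | 50.0% |
| Early stop, μ = 22 | 2.58% | 1.2% | 2.6% |
| Type I error | 5% | 2.7% | 4.9% |
| Power | 85% | 89.6% | 85.7% |

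The stated figures do not follow from the written SD of 12.02; an SD near 14 comes close. That is a separate matter, so both SDs are carried forward.

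**Step 4: chance of success when sparing adds nothing.** Here μ equals the whole-larynx fall.

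| Assumed whole-larynx fall (points) | P(success), SD 12.02 | P(success), SD 14 |
|---|---|---|
| 11 | 0.01% | 0.06% |
| 13.2 | 0.3% | 0.9% |
| 14 | 0.9% | 2.0% |
| 15 | 2.7% | 4.9% |
| 17 | 16% | 19% |
| 19 | 46% | 46% |
| 22 | 90% | 86% |

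At 15 points or below, the rule is at least as strict as the plan says. Above 15, the chance of a misleading success rises quickly: 4 points take it to nearly one in two. The pattern is the same under either SD.

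**Step 5: is 15 points documented as the historical value?** No section states a 2-year VHI score or fall after whole-larynx radiation. The remark about further decline implies some fall in the cited radiotherapy series but not its size, and it serves to justify the SD. The citations attached to the 30% and 50% figures (38 and 39) lie beyond the reference list, which ends at 33.

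**The case against.** The plan claims less than proof of superiority. Its hypothesis speaks only of results that are suggestive of improvement, the primary endpoint names no comparator, and the null is openly worded against baseline. The null is not zero change: the design allows a 15-point fall before counting any benefit and needs 19.2 to succeed. The null is also 33%, not the cited 30%, and the cited series tabulates VHI scores, so it may contain a value near 15.

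Most of this stands. A reader might infer that 15 points is too lenient and that the trial is biased towards success. The documents do not support that: nothing shows the historical fall exceeds 15, and at 14 points or fewer the chance of a misleading success is below 1% at SD 12.02. The 90% figure requires whole-larynx patients already to reach the trial's full alternative, for which there is no evidence here. Nor does the protocol assert proven superiority over whole-larynx radiation.

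What the objection does not supply is the missing link. Even a suggestion against historical controls needs a historical value, and allowing for some fall is not the same as allowing for the historical one.

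**Conclusion.** The point holds as one of interpretation and justification. The percentages that introduce the null compare techniques, the null is a change from baseline, and no section connects 15 points with the outcome of whole-larynx radiation. Rejecting the null supports the statement that mean VHI fell by more than 15 points, and no more by itself. Describing 33% as conservative is justified only if the historical fall is about 15 points or less, which is not stated.

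The size cannot be fixed from the documents. Over assumed historical falls of 11 to 22 points, the chance of success with no added benefit runs from 0.01% to 90% at SD 12.02. This rests on normally distributed means, the stated cut-offs, 30 evaluable patients, and trial patients comparable with the historical group apart from technique.

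**What to change.** Choose one of two routes.

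1. **Keep 15 points.** Word the VHI conclusion as: *mean VHI fell by more than 15 points from baseline*. Remove the functional comparison with historical controls from Sections 2.0 and 2.4. The cost is wording and a weaker claim.

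2. **Keep the comparison.** Set the null to a documented VHI fall after whole-larynx radiation. Name the source group and time point: the title of the cited series covers both conventional and hypofractionated radiotherapy, so the group must be specified. Recalculate the interim cut-off, final cut-off and power from that value. Because a historical mean carries its own uncertainty, report how the conclusion changes over a range of historical values, in the manner of the Step 4 table. Section 11.0 says the series has no 2-year score, so a neighbouring time point must be labelled an approximation; a 3-year value may overstate the 2-year fall and so make the test too strict. The cost is a search for a usable source and a recalculation. If the historical fall exceeds 15 points, the cut-off rises and the stated power falls.

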2.2 Endpoints

2.1.1 Primary endpoint

Demonstrate a 50% improvement in the VHI (voice handicap index) score at 24 months after the completion of therapy

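### The VHI hypotheses are percentage falls, but the stop and success rules are fixed point declines that match those percentages only if the baseline mean is 44

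*Combined protocol and SAP*

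**What the plan says.** Section 2.1.1 gives the primary endpoint as a percentage: "Demonstrate a 50% improvement in the VHI (voice handicap index) score at 24 months after the completion of therapy".

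Section 11.0 also states both hypotheses as percentages and then converts them to points with a planning mean:
- Null: "the null hypothesis of this analysis is that two year VHI scores will be 33% lower than baseline". Conversion: "This represents a decline from an average VHI global score of 44 to about 29, a decline of 15 points".
- Alternative: "Our alternative of interest is a 50% decline in VHI global score, a decline of 22 points".

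The rules that bind the trial are in points only:
- Interim: "We will terminate the study after the first 15 patients have been evaluated at 2 years if their average decline is less than 15".
- Final: "If the overall average of all 30 patients is at least 19.2 we will reject the null hypothesis".

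Baseline VHI is measured: "We will obtain baseline and 2 year VHI scores for an initial cohort of 15 patients", and the calendar in 9.0 has it before treatment. Neither 11.0 nor any other section adjusts the 15 or the 19.2 to the baseline mean of the patients enrolled or defines an analysis of percentage change. The eligibility criteria (4.1, 4.2) set no VHI range.

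**The concern.** A fixed number of points is a different percentage at each baseline. At a mean of 40, declines of 15 and 19.2 points are falls of 37.5% and 48.0%; at 50 they are 30.0% and 38.4%. The planning mean therefore does more than size the trial. It also determines which percentage hypothesis the rule tests.

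If the enrolled population has a lower mean VHI than 44, a treatment that truly halves VHI is too often stopped or missed. If the mean is higher, a one-third fall, which is the null, is declared a success more often than the stated 5%. The same rule decides whether the second 15 patients are recruited, in a trial that projects up to 4 patients a year (3.1).

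The issue is a population mean other than 44. Chance variation of a sample mean around 44 is already part of the SD of change.

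**Working it through.** **Inputs from 11.0.** SD of one VHI score 8.5, used at both times; SD of change 8.5 × 1.414 = 12.02, which corresponds to zero correlation between the two scores; n = 15, then 30; cut-offs 15 and 19.2. Assumed: a true baseline mean B other than 44, with the SD held at 12.02 as B changes.

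**Method.** For a true mean decline μ:
- SE at 15 = 12.02/√15 = 3.103; SE at 30 = 12.02/√30 = 2.194.
- P(early stop) = Φ((15 − μ)/3.103).
- P(success) = P(mean₁₅ ≥ 15 and mean₃₀ ≥ 19.2), bivariate normal with correlation √(15/30) = 0.707.

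**The plan's own figures, at 15 and 22 points.** The plan says: "The design has 50% chance of early stopping under the null and a 2.58% chance of early stopping in error", with type I error 5% and power 85%. The calculation gives early stopping of 50% under the null and 1.2% under the alternative, type I error 2.7% and power 89.6%. Only the 50% is reproduced. That is a separate discrepancy, and the present point does not rest on it.

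**Percentage hypotheses at other baselines.** Set μ = B/2 for a true 50% fall and μ = B/3 for a true one-third fall.
- B = 40, 50% fall: μ = 20. Stop: Φ((15 − 20)/3.103) = Φ(−1.61) = 5.4%. Final bar alone: Φ((20 − 19.2)/2.194) = Φ(0.365) = 64.2%. Jointly 63.8%.
- B = 50, one-third fall: μ = 16.67. Stop: Φ((15 − 16.67)/3.103) = Φ(−0.537) = 29.6%. Final bar alone: 1 − Φ((19.2 − 16.67)/2.194) = 1 − Φ(1.155) = 12.4%. Jointly 12.3%.

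| Baseline mean B | 19.2 points as % of B | Success, true 50% fall | Success, true one-third fall | Early stop, true one-third fall |
|---|---|---|---|---|
| 35 | 54.9% | 22% | <0.1% | 86% |
| 40 | 48.0% | 64% | 0.4% | 70% |
| 42 | 45.7% | 79% | 0.9% | 63% |
| 44 | 43.6% | 90% | 2% | 54% |
| 46 | 41.7% | 96% | 4% | 46% |
| 48 | 40.0% | 98% | 7% | 37% |
| 50 | 38.4% | >99% | 12% | 30% |
| 55 | 34.9% | >99% | 34% | 14% |

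The 54% at B = 44, against the stated 50%, is rounding (44/3 = 14.67, written as 15) and not a baseline effect.

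The same true 40% fall succeeds 7% of the time at B = 40, 23% at 44 and 64% at 50.

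**Range in which the rule works.** Power of at least 85% needs B of about 43.0 or more; error of at most 5% needs B of about 46.8 or less. With an assumed correlation of 0.5 (SD of change 8.5) the range is 41.6 to 49.9. With an SD of 14, which roughly reproduces the stated error rates, it is 43.8 to 45.1.

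**The case against.** The strongest reply is that 11.0 states the hypotheses in points as well. On that reading the rule tests 15 against 22 points at any baseline, and what remains is an ordinary planning assumption and a percentage label in 2.1.1. The points rule is indeed coherent in itself, and the conversion is disclosed. But 11.0 gives the points null only as what a 33% fall amounts to from an average of 44, and 2.1.1 gives a percentage alone. Declaring the hypotheses in points would remove the inconsistency, but it would also give up the percentage endpoint.

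A second reply is that no document gives a baseline mean other than 44, and that the largest effects, at 35 and 55, lie more than one between-patient SD away. This stands as a limit on the size of the harm. Holding the SD fixed is also an assumption, and the width of the workable range depends on the SD: about 1 point at SD 14, about 4 at 12.02 and about 8 at 8.5. The direction of the effect is the same at all three.

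A third reply is that the 43.6% rule does not restore a 5% type I error. That is true: at baseline 44 its error is about 0.5%, and success under a true 40% fall goes from 23% to 18%. It is conservative, and its error still varies with baseline.

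**Conclusion.** The concern holds and should be fixed. The endpoint, null and alternative are percentages of baseline VHI. The rules are fixed points that correspond to those percentages only near a mean of 44. With the plan's SD of change, error of at most 5% together with power of at least 85% holds only for baseline means of about 43.0 to 46.8.

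Confidence in the mismatch is high. The size of the harm is conditional: it depends on a baseline mean that the documents do not give, on an SD that stays constant across baselines, and on the correlation between the two scores. If the mean is within 2 points of 44 the effect is modest.

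**What to change.** Before two-year data are seen, amend 11.0 so that the cut-offs follow the observed baseline:
- At 15 patients, stop if the mean decline is below one third of the mean baseline VHI of those 15.
- At 30 patients, reject the null if the mean decline is at least 43.6% (19.2/44) of the mean baseline VHI of all 30.

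Restate the operating characteristics in 11.0. In 2.1.1, say that the trial tests for a fall in mean VHI of more than one third, with 50% as the design alternative. Report the estimated percentage fall, 1 − (mean 24-month VHI / mean baseline VHI), with a confidence interval.

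At SD 8.5 and correlation 0, for baseline means of 30 to 60, this rule has early stopping under the null of 50%, type I error of about 4% or less and power of at least 85%.

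**Cost.** Wording only: the same two VHI scores, the same 30 patients, no extra visits. At a baseline of 44 the success bar stays at 19.2 and the interim bar moves from 15 to 14.7 points. The success bar becomes 17.5 points at 40 and 21.8 at 50. The rule still relies on the SD of 8.5: with an assumed SD of 12 at each time and correlation 0, type I error is 7% at baseline 35 and 3.5% at 44, with power 80% and 86%.

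**Option.** If type I error near 5% at every baseline matters more than keeping the present bar, use W = (2/3) × baseline VHI − 24-month VHI. Stop at 15 if mean W is below 0, and apply a one-sided 5% t-test at 30. Simulated type I error is 4.8% to 5.0% for baselines of 30 to 60, and it does not rely on a planning SD. The downside is a lower bar. At baseline 44 the bar is 1/3 + t(0.95, 29 df) × SD(W)/√30/44, an observed fall of about 40.5% (38.6% with correlation 0.5). A true 40% fall then succeeds 45% of the time, against 23% under the rule as written and 18% under the 43.6% rule.
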